Control group: healthy patients 39 healthy controls

PCO:

Population: Oral Lichen Planus patients.

Control: Healthy patients.

Outcomes: Salivary and serum leptin levels.

8. Settings

All patients will be selected from the "out-patient clinic" of Oral Medicine – Oral Diagnosis and Periodontology Department; Faculty of Dentistry, Cairo University.

All controls will be selected from the "out-patient clinic" of any clinical department other than Oral Medicine; Faculty of Dentistry, Cairo University.

B) Participants

9. Eligibility criteria and selection methods

Inclusion criteria:

- Ages for both sexes fall between 30 and 70.
- Symptomatic OLP has been diagnosed clinically and verified histologically.
- Participants who sign a written consent form after being fully informed about the study

Exclusion criteria:

- Treatment with a systemic or locally administered systemic medication within the previous three months before the commencement of the research.

- Patients now taking or who have just stopped taking an NSAID (both steroid and non-steroidal) for pain or inflammation.
- Patients who have been diagnosed with a malignant tumor or tumors.
- Women who are expecting or nursing.
- Inmates, the mentally ill, the elderly, etc., all fall into this category.

rationale for choosing cases and controls for case control studies

All patients will undergo a thorough history and physical examination, and an incisional biopsy of the oral lesion will be taken for histological analysis to confirm a diagnosis of Oral Lichen Planus.

In order to make a fair comparison of salivary and serum leptin levels between cases and controls, we will select individuals who do not have any systemic or oral lesions.

10. Matching criteria and allocation ratio

Matching will be according to Age and Gender

The ratio between cases to controls is 1:1

C) Variables

11. Details about variables

Outcomes: Salivary and serum leptin levels.

Potential confounders: Age and Gender, Type of OLP

Diagnostic criteria: presence of Oral Lichen Planus form(s) (Reticular, Atrophic or Bullous-Erosive forms)

12. Data sources and management

Salivary and serum leptin levels Measurement.

-For patients in Group I, we will collect a saliva sample. Saliva and serum samples from participants in Group II (healthy controls) will be frozen at -80 degrees Celsius until ELISA testing can be performed.

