A power analysis was created to have enough strength to use a two-sided statistical test of the null hypothesis that there is no difference between tested groups regarding salivary and serum leptin levels. By adopting an alpha (α) level of 0.05 (5%), a beta (β) level of 0.2 (i.e. power=80%), and an effect size (d) of (0.736) calculated based on the results of a previous study.¹; the predicted total sample size (n) was found to be (62) cases (i.e. 31 cases per groups). Sample size was increased by (25%) to compensate for possible drop-out during different follow up intervals to be a total of (78) cases (i.e. 39 cases per group). Sample size calculation was performed using G*Power version 3.1.9.7²

14. Study size

Cases: 39... patients

Controls: 39.... Subjects,

E) Quantitative variables

15. Handling of quantitative variables in the analysis

Variables: Oral Lichen Planus disease, types and duration

Potential confounders: Age and Gender, personal habits

Patients will be grouped according to the disease and Outcomes. Potential confounders will be taken into consideration.

F) Statistical methods

16. Statistical methods

Categorical data will be analysed using the chi square test and given as frequency (n) and percentage (%). By examining the distribution of the data, computing the mean and median values, and applying the Kolmogorov-Smirnov and Shapiro-Wilk tests, numerical data will be examined for normality. If the data were found to be normal, the mean and standard deviation values would be reported, and an independent t-test would be used to compare the groups. The data will be given as median and range values if the assumption of normality is broken, and the Mann-Whitney U test and Friedman's test will be used to compare the groups. For all tests, the significance threshold will be set at P 0.05. With IBM® SPSS® Statistics Version 25 for Windows, statistical analysis will be carried out.

IV. Ethics and dissemination:

17a. Research ethics approval

The protocol will be proposed to the ethics committee of faculty of dentistry, Cairo University

17b. Protocol amendments

No amendments are planned; however, if any amendment was formed, it will be published as amendments to the pre-published protocol

17c. Informed consent

All participants in the study will be asked to provide an informed signed consent after full understanding of the study procedure and before allocation in the study.

17d. Confidentiality

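### For non-normal data, Section 16 compares cases with controls by both Mann-Whitney U and Friedman's test, names neither as deciding, and defines none of the blocks that Friedman's test needs

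*Combined protocol and SAP*

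**What the plan says.** Section 16 (Statistical methods) is the only analysis text. If data look normal, "an independent t-test would be used to compare the groups". If they do not, "the Mann-Whitney U test and Friedman's test will be used to compare the groups". One threshold covers everything: "For all tests, the significance threshold will be set at P 0.05". No sentence ranks the two rank tests, gives them different outcomes, or says what follows if they disagree.

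The places that might supply the structure Friedman's test needs are these:

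- Section 7 (Study design) has two groups, cases and healthy controls, 39 in each.
- Section 10 (Matching criteria and allocation ratio) says "Matching will be according to Age and Gender" and "The ratio between cases to controls is 1:1". It does not say whether each control belongs to a particular case or whether the groups are only balanced overall.
- Section 12 (Data sources and management) describes saliva and blood collection and schedules no repeat sample.
- Part D (Study size) justifies its allowance by "possible drop-out during different follow up intervals". No follow-up visit appears anywhere else.
- Section 15 adds only "Potential confounders will be taken into consideration", with no method attached.

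The research question in Section 1 makes serum leptin the primary outcome.

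**The concern.** Two tests are given the same job at the same threshold, and one of them does not fit the design as written. Friedman's test ranks values within blocks of related observations. A comparison of two independent groups has no such blocks.

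The statement on matching does not settle this, because each reading of it leaves Section 16 inconsistent. If matching is not individual, the blocks would be whatever case and control happen to share a row of the spreadsheet, and the result would depend on row order. If matching is individual, the pairs are legitimate blocks, but the Mann-Whitney test and the independent t-test named beside Friedman's test ignore them.

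What is at stake is the main result. If serum leptin is judged non-normal, the analyst will hold two p-values and no rule for which one answers the research question, so the choice would be made after seeing them.

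**Working it through.** **1. The plan's own sample size.** Inputs from part D: two-sided alpha 0.05, power 80%, d = 0.736, 31 per group, raised by 25% to 39.

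- Two-sample t-test (noncentral t): 29.97, so 30 per group.
- Mann-Whitney, dividing by its efficiency of 3/π for normal data: 29.97 × π/3 = 31.4, so 32 per group.
- Inflation: 62 × 1.25 = 77.5, so 78 in total.

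The stated 31 lies within one of both results, so the sample size reproduces. It rests on an unpaired two-group comparison.

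**2. What Friedman's test becomes with two columns.** Let n be the number of row pairs and S the number in which the case value is higher. The rank sums are n + S and 2n − S. Then

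χ² = (2/n)[(n + S)² + (2n − S)²] − 9n = (2S − n)²/n, on 1 degree of freedom.

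This is a sign test. It uses only the direction of each difference.

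**3. Exact size and power of that test** (critical value 3.84).

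- n = 39: S = 26 gives 13²/39 = 4.33, and S = 25 gives 11²/39 = 3.10. It rejects for S ≤ 13 or S ≥ 26. Exact size 5.3%.
- n = 31: S = 21 gives 11²/31 = 3.90, and S = 20 gives 9²/31 = 2.61. It rejects for S ≤ 10 or S ≥ 21. Exact size 7.1%.
- With arbitrary pairs and d = 0.736, P(case > control) = Φ(0.736/√2) = 0.699. Binomial power is 73.3% at n = 39 and 68.2% at n = 31.

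**4. Mann-Whitney power, unmatched.** Using an effective n of 39 × 3/π = 37.2 and 31 × 3/π = 29.6 in the noncentral t gives 88.0% and 79.5%.

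**5. The two tests together.** These are simulations with normal data and two-sided alpha 0.05. Within-pair correlations are assumptions, because the documents give none. Entries are for 39 / 31 per group, rounded.

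| Setting | Mann-Whitney power | Friedman power | Tests disagree (d = 0.736) | Type I error if either counts |
|---|---|---|---|---|
| No effective matching | 88% / 80% | 73% / 68% | 18% / 18% | 8% / 9% |
| Individual pairs, correlation 0.3 | 92% / 83% | 87% / 82% | 10% / 14% | 6% / 8% |
| Individual pairs, correlation 0.5 | 94–95% / 87% | 95% / 92% | 6% / 11% | 5.5% / 7% |

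Separate runs of the unmatched either-test figure ranged from 7.4% to 8.0% at 39 and from 8.9% to 9.3% at 31.

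With no effective matching at 39 per group, the usual conflict is Mann-Whitney significant alone (16.1%). Friedman is significant alone in 1.7%.

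If groups are frequency-matched on a factor that explains 10%, 30% or 50% of the variance (also assumed), the either-test error at 39 per group is 6.6%, 4.0% and 1.9%. It is not inflated when the matching factor is strong.

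**The case against.** The best defence is that Section 10 supplies the pairs, so Friedman's test is legitimate. That would be true if matching were individual, but the plan does not say so, and the unpaired tests in the same section point the other way. The ambiguity has to be resolved whichever reading was meant.

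A second defence is that the test was meant for something else. Saliva and serum give two related values per participant, and the follow-up wording in part D hints at repeated measures. Either may explain how the test came to be there. Neither makes it a test of cases against controls, which is the purpose that the sentence states. Nor does the drop-out wording show that repeat visits were planned and left out.

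Three stronger readings are tempting, and the documents do not support them:

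- **The plan inflates type I error.** A reader might infer this from two tests at one threshold. The plan never says that significance on either is enough. The 8% and 9% describe a hypothetical rule, and strong frequency matching removes the inflation.
- **The study's power is wrong, or is comfortably safe.** The first does not follow, since the sample size reproduces. The second does not follow either: 88% holds only if all 39 per group are analysed, and at the evaluable 31 Mann-Whitney has 79.5%.
- **Ignoring the matching makes Mann-Whitney invalid.** Under effective matching it is conservative. Adjusting for the factors under frequency matching is an optional gain in efficiency and a separate question.

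One limitation stands. The figures use normal data, while the two-test sentence applies only when normality fails. They carry over only if d = 0.736 holds on some normalising scale.

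**Conclusion.** The wording defect is certain and should be fixed. In the non-normal branch, Section 16 prescribes two tests for one comparison, ranks neither, and includes one whose required structure the plan never defines. This bears directly on the primary outcome.

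Its size depends on how matching is done and on how many participants are analysed. With no effective matching, roughly one dataset in six at the planned effect would give conflicting answers. Effective individual pairing lowers that at both sample sizes, and more at 39 pairs than at 31. These figures illustrate the consequence and do not estimate an error rate for this study. The finding is an unspecified deciding test and an ill-fitting second one, not a demonstrated loss of error control or a flaw in the sample size.

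**What to change.** 1. In Section 16, delete Friedman's test from the comparison of cases with controls.
2. In Section 10, state whether matching is individual or by frequency.
3. In Section 16, name one deciding test for the non-normal branch before any data are seen:
   - If pairs are not kept, Mann-Whitney U, the counterpart of the independent t-test already stated.
   - If matching is individual, the Wilcoxon signed-rank test, with a paired t-test on the normal branch and a pair identifier in the dataset. The signed-rank test assumes roughly symmetric within-pair differences.

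The cost is one sentence in Section 10 and one or two in Section 16, with no extra participants or samples. Keeping pairs adds one data column, and any pair that loses a member drops out of the paired tests. If 8 were lost from each group (39 − 31) and all fell in different pairs, 39 − 16 = 23 complete pairs would remain, so this should be weighed before pairing is chosen. How normality is judged, and so which branch applies, is a separate matter that this change does not settle.
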